8.5 COMPLIANCE TO STUDY TREATMENT

During each cycle (defined from the day of current visit to the day before the next visit), a patient will be considered to be compliant with therapy if s/he takes at least 8 of the 9 capsules of study drug provided in the clinical study medication kit and at least 6 of the 7 AZA administrations (as a consequence, cycles with interruptions due to AEs are not included).

Compliance with therapy (number of patients compliant/non-compliant; percentage of compliant patients) will be summarized by cycle and by treatment group for pracinostat / placebo and for AZA.

Compliance over the whole study period will also be summarized.

A patient is regarded as compliant with therapy overall, if the ratio between the total number of capsules of study drug (pracinostat/placebo) taken and the total number of capsules expected for all the cycles performed (excluding drug-holiday period and interruptions due to AEs) for this patient is $\geq 8/9$ and the ratio between the total number of administrations of AZA and the total number of administrations expected for all the cycles performed

(excluding drug-holiday period and interruptions due to AEs) for this patient is $\geq 6/7$. Overall compliance will also be presented split by study drug and AZA.

The analysis set will be the ITT set.

All compliance data will be provided in data listings.

9 SAFETY

The SAF set will be used for all the analyses of safety data.

9.1 EXPOSURE TO STUDY TREATMENT

Exposure and drug dosing compliance will be summarized with descriptive statistics by treatment group. All exposure data will be provided in data listings. Exposure will be calculated for the overall study separately for pracinostat/placebo and AZA and analyzed by means of descriptive statistics:

- As treatment period duration: the end of the treatment period within one cycle is not documented in the CRF, the period duration for patients still on study treatment is therefore calculated as the scheduled last dose date minus the first dose date plus 1. For patients who already finished the treatment period, the duration of the whole study period is calculated as date of last treatment dose (pracinostat/placebo as documented in the subject disposition page of the CRF) minus the date of the first treatment (pracinostat/placebo) plus 1.
- As cumulative administered dose (summing up all the actual doses in mg). If computation is to be performed when information on current cycle is still not available (as the respective data are collected at start of the next cycle), the dose for the actual cycle will be estimated based on planned scheduling.
- As percent relative cumulative administered dose (cumulative administered dose (mg) / expected cumulative administered dose (mg) x 100). Expected dose will be based on the dose to be administered (i.e. 60 mg for pracinostat/placebo and 75mg/m² BSA for AZA) independently from any reduction or modification that occurred (however, drug holiday will not be included). The BSA used for the calculations will be the one measured at start of each cycle, according to protocol scheduling.
- As cumulative number of administrations.
- As cumulative number of cycles with treatment (either partial or complete). Description by categories might also be considered at time of BDRM.
- As absolute and relative frequency (percentage) of patients who reduced the dose (two possible reductions for AZA), of patients who had permanent discontinuation of treatment and of patients who interrupted treatment temporarily (overall and by reason of interruption) and patients who had drug-holiday.

AZA administration route will also be reported according to the following classification:

- IV infusion for entire study

-
- SC injection for entire study
 - Switched between IV infusion and SC injection 1 time during study
 - Switched route more than 1 time during study

Scheduling will also be categorized, based on actual administration dates, as follows:

- Number of patients on Azacitidine schedule 1 (consecutive 1-7 days) entire study
- Number of patients on Azacitidine schedule 2 (5-2-2) entire study
- Number of patients switching between 1-7 and 5-2-2 or viceversa during study
- Alternative schedules

In order to classify patients, first each cycle will be categorized as above described, then patients will be classified after exclusion of cycles with a number of administrations less than 7.

Data collected for the possible cases of drug-holiday will be listed.

9.2 ADVERSE EVENTS

The analyses of safety will be performed on the SAF set.

Adverse events will be coded to the Preferred Term (PT) level using the Medical Dictionary for Regulatory Activities. Version used at the start of the study will be the most recent one published (current version 20.0), and will be used until the end of the study.

The NCI CTCAE grade for each adverse event will be documented by the treating physician in the eCRF.

A by-patient AE (including treatment-emergent, pre-treatment and post-treatment (if any)) data listing including verbatim term, PT, SOC, NCI CTCAE grade, and relationship to study treatment (AZA and Pracinostat/placebo) will be provided.

Deaths, SAEs, including those leading to death, and adverse events leading to discontinuation of study treatment or of special interest will be listed.

All AEs regardless of when they were reported will be listed.

9.2.1 Pre- and post-study adverse events

Pre-treatment AEs and post-treatment AEs (if any) will be listed.

Pre-treatment AEs are defined as adverse events starting before the first dose of pracinostat/placebo is given, and which did not worsen during treatment period.

Post-treatment AEs are defined as adverse events starting after the end of the observation period, which is defined as 30 days after the last dose of pracinostat/placebo, or start of a new therapy for AML, whichever occurs first.

However, to avoid missing important AEs, also AEs started within 30 days after last dose of pracinostat/placebo after start of a new therapy for AML will be considered as post-treatment events but will be flagged within the related listing.

9.2.2 Treatment emergent adverse events (TEAEs)

Treatment-emergent AEs (TEAEs) are defined as AEs with onset date/time at or after the start date/time of the first intake of pracinostat /placebo, or AEs with onset date/time prior to start date/time of the first intake of pracinostat/placebo that worsen in severity after the start date/time of the first intake of pracinostat /placebo, up to the end of the observation period. The observation period is defined as 30 days after the last dose of pracinostat/placebo or start of a new therapy for AML, whichever occurs first. TEAEs will be summarized by treatment group.

Where dates and/or times are missing or partially missing, AEs will be considered treatment emergent, unless there is clear evidence (through comparison of partial dates and/or times) to suggest that the AE started prior or after the study period.

The following tables will be produced:

- An overview summary of TEAEs by treatment group, including counts and percentages of patients as well as the number of events. The summary includes the following kinds of AEs:
 - any TEAE;
 - TEAEs by worst NCI CTCAE grade (only number of patients and %)
 - TEAEs by NCI CTCAE grade
 - TEAEs causally related to study drug / AZA / study drug or AZA (i.e either component of the study treatment);
 - TEAEs leading to permanent discontinuation of study treatment;
 - TEAEs leading to interruption of study treatment (separately for study drug and AZA)
 - TEAEs leading to dose reduction
 - SAEs;
 - SAEs causally related to study drug / AZA / study drug or AZA;
 - fatal SAEs;
 - fatal SAEs causally related to study drug / AZA / study drug or AZA
 - TEAEs of special interest
 - TEAEs of special interest related to study drug
- The number and percentage of patients reporting TEAEs will be provided by treatment group, System Organ Class (SOC), Preferred Term (PT), worst NCI CTCAE grade, and total. TEAEs will be sorted by SOC and PT in alphabetical order (SOC and PT within SOC).
- The number and percentage of patients reporting TEAEs together with the number of AEs, will be provided by treatment group, SOC, PT, and total. Similar table will be provided including only ≥ 3 worst NCI CTCAE grade. TEAEs will be sorted by frequency (based on column Total of all AEs) of a SOC and the PTs within a SOC.
- The number and percentage of patients reporting study drug (pracinostat / placebo) related (as classified by investigator) TEAEs will be provided as described for “all

-
- TEAEs” in previous bullet. Missing relationship to study drug will be regarded as related. The number and percentage of patients reporting AZA related (as classified by investigator) TEAEs will be provided as described for “all TEAEs” in previous bullet. Missing relationship to AZA will be regarded as related.
- The number and percentage of patients reporting TEAEs either study drug (pracinostat / placebo) or AZA related (as classified by investigator) will be provided as described for “all TEAEs” in previous bullet. Missing relationship to at least one of the two components of treatment (study drug or AZA) will be regarded as related.
 - The number and percentage of patients reporting TEAEs of special interest (AESIs) will be provided by treatment group, type of AESIs, PT, worst NCI CTCAE grade, and total. TEAEs will be sorted by type of AESI and PT in alphabetical order (AESI and PT within AESI). The same summary table will be provided including only TEAEs related to study drug (pracinostat / placebo). Missing relationship to study treatment will be regarded as related.
 - The number and percentage of patients reporting TEAEs of special interest together with the number of AEs, will be provided by treatment group, type of AESIs, PT, and total. Similar table will be provided including only ≥ 3 worst NCI CTCAE grade. TEAEs will be sorted by frequency (based on column Total of all AEs) of a AESI and the PTs within a AESI. The same summary table will be provided including only TEAEs related to study drug. Missing relationship to study drug will be regarded as related.

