8.2 Adverse Event Reporting

All adverse events occurring from the informed consent signature until 30 calendar days after last study drug (pracinostat/placebo) intake, or until the initiation of new therapy for AML, whichever occurs first, are to be recorded on the appropriate eCRF section.

Every effort must be made by the Investigator to categorize each adverse event according to its severity and its relationship to the study treatment (study drug and/or azacitidine).

All AEs will be followed until symptom resolution or until the condition stabilizes, unless, in the Investigator's opinion, the AE or laboratory abnormality/ies are not likely to improve because of the underlying disease or unless the patient is lost to follow-up.

Whenever a change in the severity of an AE (such as a worsening) has occurred, a follow up of the initial AE should be entered in the eCRF reporting the new severity.

Outcome of ongoing serious and non-serious AEs will be reported in eCRF until the end of the reporting period as above defined. All non-resolved serious and non-serious AEs beyond such date will be recorded in eCRF as "ongoing" without further follow-up.

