6.4 DATA DERIVATIONS AND DEFINITIONS

When reporting durations in months, divide the number of days by 30.4375; to report in weeks divide the number of days by 7; to report in years divide the number of days by 365.25. These algorithms for durations / time to event return decimal numbers, and ignore the actual numbers of days in the months or years between start date and stop date. The "year" used in these algorithms is 365.25 days long, and the "month" is one twelfth of that year.

Durations and time to events will be analyzed in days.

Baseline is defined as measurement obtained at the most recent assessment prior to the date of the first study treatment dose. Change from baseline will be calculated as the difference between the respective visit value and the baseline value.

Age will be calculated from the date of birth to Screening date.

For the calculation of exposure to study drug the Body Surface Area (BSA) is needed. If the baseline BSA is not documented, the next available documented BSA within the study period will be used for the calculation of the exposure.

The following will define pre-treatment use versus concomitant medication use:

- Prior use ending before receiving the first administration of study drug will be defined as "pre-treatment medications".
- Medications that started prior to the first administration of study drug, and continued pass through the first administered dose date as well as medication started after the first administered dose date will be defined as concomitant medications.

In a similar way, prior and concomitant procedures will be defined as:

- Prior procedures ending before receiving the first administration of study drug will be defined as "prior procedures".

- Procedures that started prior to the first administration of study drug, and continued pass through the first administered dose date as well as procedures started after the first administered dose date will be defined as concomitant procedures.

TEAEs will be considered as any event occurring, or a pre-existing event worsening, on or after receiving the first intake of pracinostat /placebo, and up to 30 days after receiving the last administration of study drug (date reported in the field Date of Last Pracinostat/Placebo Administration in the Subject Disposition page of the CRF will be used as the reference point).

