- The number of surviving patients, the number of deaths and the number of patients with censored values will be displayed as well.
- Censoring patterns will be examined between treatment groups. Therefore the censored and not censored observations in the two treatment groups will be analyzed over time in a scatterplot.
- The effect of subsequent therapy on OS will be analyzed, including an analysis that compares OS in the treatment groups with censoring at the start date of the new interceding therapy, including those started during study treatment phase (concomitant therapy) and after stopping of study treatment as recorded in the new AML therapy eCRF page. Balance of such cases in the two treatment groups will be assessed to evaluate the appropriateness of this analysis method.
- Other sensitivity analyses will be performed to assess the robustness of OS results, if relevant. These will be decided prior to unblinding (e.g. at BDRM) based on real data.
- The primary OS analysis (stratified log-rank test) will be repeated for the PP set.
- Impact on OS of other baseline/demographic factors (including those considered for the subgroup analysis (section 5.3), plus possible others), will not be evaluated by means of Cox PH model(s) as initially planned due to the evident lack of the PH assumption for the treatment group factor.

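### SAP 6.4 and SAP 9.2 define the TEAE window differently once a new AML therapy starts, and the 9.2 rule does not require that study drug has stopped

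*SAP*

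**What the plan says.** **First definition.** SAP 6.4 counts an event that occurs or worsens "on or after receiving the first intake of pracinostat /placebo, and up to 30 days after receiving the last administration of study drug". It names the CRF field for the last pracinostat/placebo date as the reference point and does not mention new AML therapy. The same section then derives one summary record per TEAE, to be used for the summary tables.

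**Second definition.** SAP 9.2.2 says that the "observation period is defined as 30 days after the last dose of pracinostat/placebo or start of a new therapy for AML", whichever of the two is earlier. Its list of AE tables follows. SAP 9.2.1 uses the same end-point to define post-treatment events, which are listed only. It adds that events after a new therapy but within 30 days of the last dose "will be considered as post-treatment events but will be flagged within the related listing".

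**Protocol.** Section 8.1.1.5 ends the TEAE window with the AE reporting period. Under section 8.2, events up to 30 days after the last intake "or until the initiation of new therapy for AML, whichever occurs first, are to be recorded". Section 8.2.1 (SAEs) and footnote U of the schedule of assessments carry the same stop. The End of Treatment visit (5.1.14) has AEs assessed to 30 days after the last intake and states no stop for AE assessment at new therapy.

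**New therapy during study treatment.** The SAP makes room for it. In SAP 8.1.2, the OS analysis that censors at interceding therapy covers therapies "including those started during study treatment phase (concomitant therapy) and after stopping of study treatment". SAP 8.2 also takes interceding therapies from the concomitant medication page, and Listing B15 is set aside for prior or concomitant drugs treated as new AML therapy.

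**The concern.** There are two separate defects.

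The first is a contradiction. Both sections lay claim to the tables: 9.2.2 lists them, and 6.4 builds the record from which they are made. No sentence says which governs. Two programmers following the same SAP could produce different counts in the TEAE, related-TEAE, special-interest, treatment-emergent SAE, fatal treatment-emergent SAE, by-cycle and subgroup tables.

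The second is a missing condition. The 9.2 rule lets a new AML therapy close the window whether or not study drug is still being taken. Section 9.2 does not define new therapy for AML. The exceptions in SAP 7.8 (courses of up to 3 days, therapies that start and end before Cycle 1 Day 15, the widened hydroxyurea allowance) are written for censoring in time-to-event analyses and are not carried over to safety. Hydroxyurea, which the protocol permits up to Cycle 1 Day 14, is therefore not expressly prevented from closing the window in the first cycle. Events on study drug are the ones a TEAE table exists to show.

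**Working it through.** The plan states no figure on this point, so there is none to reproduce. The check compares the two definitions as date rules.

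**Inputs.** L = day of last pracinostat/placebo dose; N = day a new AML therapy starts.

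- SAP 6.4: window closes on day L + 30.
- SAP 9.2.1, 9.2.2 and protocol 8.2: window closes on day min(L + 30, N).
- Days by which the definitions differ: max(0, L + 30 − N).
- Days of study drug treatment outside the 9.2 window: max(0, L − N).

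**Illustration.** First dose on day 1 and L = 100. These day numbers are assumptions, not document values.

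| Case | N | 6.4 closes | 9.2 closes | Difference (days) | Days on drug outside 9.2 window | Example AE |
|---|---|---|---|---|---|---|
| No new therapy | none | 130 | 130 | 0 | 0 | Day 120: TEAE under both |
| New therapy after last dose | 110 | 130 | 110 | 20 | 0 | Day 120: TEAE under 6.4 only |
| New therapy while on drug | 60 | 130 | 60 | 70 | 40 | Day 80: TEAE under 6.4 only |
| Start date imputed to day 1 | 1 | 130 | 1 | 129 | 99 | Day 15: TEAE under 6.4 only |

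The definitions agree unless N falls before L + 30. When the patient switches after stopping study drug, the difference cannot exceed 30 days. When the therapy is recorded during treatment, the 9.2 window loses all remaining on-drug time as well as the 30 days.

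**Imputed dates.** The last row applies only if the SAP 6.1.1 imputation of new-therapy start dates is also used for safety, which the SAP does not say. Those rules differ by arm. With only the day missing, the date is generally the first of the month for pracinostat and the last of the month for placebo. In a 31-day month the same partial date would close the window 31 − 1 = 30 days earlier for pracinostat. With the whole date missing, it is the start of study treatment for pracinostat and 1 January of that year for placebo, so either window would close on or before the first dose. The rules were chosen to be conservative for efficacy censoring, and that reasoning does not carry over to a safety window.

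**Reach of the flag in 9.2.1.** It covers events within 30 days after the last dose. Read literally, an event after the new therapy but before the last dose is post-treatment and is not covered by the flag.

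**The case against.** The case for leaving the rule alone has four parts.

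- **The governing rule is fairly clear.** Protocol 8.1.1.5, 8.2, 8.2.1 and footnote U, with SAP 9.2.1 and 9.2.2, all stop at new AML therapy. Only 6.4 differs. This stands: 6.4 is the outlier, but it still has to be corrected because it defines the record behind the tables.
- **Overlap should be rare.** Protocol 4.7.3 requires study treatment to stop before another anticancer agent is given, and 4.5.3 takes a patient who receives other AML therapy during a drug holiday out of the active phase. SAP 6.1.1 describes new therapies as starting after, or together with, the stop of study treatment. This also stands: on-drug closure should come mainly from deviations or from how a concomitant drug is classified. It limits the number of patients; it does not supply the missing condition, and SAP 8.1.2, 8.2 and Listing B15 provide for such cases.
- **The events are not hidden.** SAP 9.2 lists all AEs, 9.2.1 flags those after a switch, and 9.2.5 summarises deaths by treatment and cause without restriction to the TEAE window. A reader might infer that the affected events disappear from the report, or that fatal events appear in no table. The documents do not support that. The events leave the TEAE tables and so the tabulated comparison between arms.
- **Cutting after discontinuation is a legitimate choice.** It keeps toxicity of the next therapy out of the TEAE counts. A reader might infer that the cut should be abolished. That does not follow: it is a debatable trade-off, and sites were told to stop recording at the new therapy, so later events may be incomplete.

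**Conclusion.** Both defects hold on the text. SAP 6.4 contradicts SAP 9.2.1, SAP 9.2.2 and the protocol for any event that starts after a new AML therapy and within 30 days of the last dose. The 9.2 rule also has no off-drug condition and no safety definition of new AML therapy. For the probably few patients with an AML therapy recorded during study treatment, possibly including permitted Cycle 1 hydroxyurea, events on study drug would leave the TEAE tables.

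The size is unknown. The documents give neither the number of patients who switch within 30 days nor the number with overlapping therapy. A reader might infer that the safety comparison is biased, because switching follows progression or intolerance and may differ between arms. The documents show neither a difference nor its direction, and the trial is double-blind. A reader might also build a large loss from one example: a patient with a concomitant AML therapy from the start of Cycle 2 to the end of Cycle 6 would lose 5/6 = 83% of AE time. That is one hypothetical patient on a therapy that protocol 4.7.3 prohibits alongside study drug, not an estimate for the trial.

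The point should be corrected because the ambiguity affects most AE tables and the SAP wording is cheap to repair.

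**What to change.** 1. Use one TEAE definition in SAP 6.4, 9.2.1 and 9.2.2.
2. State that the window never closes before the last dose of pracinostat/placebo, so that a new AML therapy can shorten only the 30-day post-dose period.
3. Say which therapies count as new AML therapy for safety, including how hydroxyurea and short courses are treated, and whether the arm-specific imputed start dates of SAP 6.1.1 apply. They should not.
4. Add a supportive TEAE table to 30 days after the last dose regardless of new therapy, with events after the new therapy flagged and counted separately.
5. Reconcile protocol 8.2, 8.2.1 and footnote U so that AEs are recorded for as long as study drug is being taken.

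The cost is SAP wording, one flag variable, one extra table and a protocol clarification. A few events due to the concomitant AML therapy will enter the TEAE tables. The protocol change cannot recover events that sites did not record, so the supportive table needs a caveat on incomplete collection after a new therapy. SAP section 11 says this version was prepared after the interim results were unblinded; the change should be logged there with its timing.
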